- There will be 6 safety telephone call visits at Days 8, 29 (except for those participants in the immune response biomarker subset which requires a clinic visit on Day 29), 91, 181, 271, and 361 (Month 12)/end of study as specified in the Schedule of Events.
- Approximately 1000 participants will be asked to provide blood samples at baseline and on Day 29 (28 days post vaccination) for assessment of immune responses to the study intervention, including anti-HA antibody responses to vaccine-matched strains (immune response biomarker subset). A clinic visit on Day 29 will be required for these participants.
- All participants will be asked to complete an electronic diary (eDiary) for solicited adverse reactions (ARs) from Day 1 to Day 7.

Number of Participants: Approximately 23,000 participants will be enrolled.

Note: Enrolled means participants' agreement to participate in a clinical trial following completion of the informed consent process and screening. Potential participants who are screened for the purpose of determining eligibility for the study, but do not participate in the study, are not considered enrolled, unless otherwise specified by the protocol. A participant will be considered enrolled if the informed consent is not withdrawn prior to participating in any study activity after screening.

Study Arms and Duration:

- The study will comprise 2 study arms: investigational vaccine (mRNA-1010) group and active comparator (licensed quadrivalent inactivated seasonal influenza vaccine) group.
- The total study duration (including screening) for each participant is up to 13 months.

Data Safety Monitoring Board:

A Data Safety Monitoring Board (DSMB) will be used throughout the conduct of this study. This committee will be composed of independent members with relevant therapeutic and/or biostatistical expertise to allow for the ongoing review of safety data from this study population. Safety data will be reviewed according to intervals defined in the DSMB charter and will also occur as needed.

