1.2. Schedule of Events

Table 1: Schedule of Events

Visit Number		1	2	3	4	5	6	7	USV
Type of Visit/Contact	C	C	SC	C ¹ /SC	SC	SC	SC	SC	C
Month Timepoint				M1	M3	M6	M9	M12	Up to M12
Study Visit	Screening ²	D1 (Baseline)	D8	D29	D91	D181	D271	D361/EoS	USV
Window Allowance (Days)	-28	N/A	±2	-7 to +3	±5	±14	±14	±14	N/A
Informed consent form, demographics, vaccination and, medical history ³	X								
Inclusion/exclusion criteria	X	X							
Physical examination ⁴	X								
Vital signs ⁵	X	X							
Pregnancy testing ⁶	X	X							
Randomization		X							
Blood collection for immune response biomarkers and/or transcriptomics (optional) subset ⁷		X		X					
Blood collection for future research sample (optional) ⁸		X							
Study vaccination (including 30-minute post-dosing observation period) ⁹		X							
Collection of EFS ¹⁰		X							
NP swab for virus detection ¹¹									X
Follow-up safety call			X	X ¹²	X	X	X	X	
eDiary activation for recording solicited ARs (7 days) ¹³		X							
Review of eDiary for solicited ARs ¹⁴			X						
Symptom Reporting eDiary activation ¹⁵		X							
Symptom Reporting eDiary for collection of symptoms of ILI ¹⁶		Twice weekly from Day 1 to Day 181					Once weekly from Day 182 to Day 361		
Review of Symptom Reporting eDiary		Review participant recorded ILI starting on Day 1 through Day 361 (Month 12)/EoS							
Telephone/electronic contacts to remind participants of ILI eDiary reporting ¹⁷		Once weekly from Day 1 to Day 181					Every 2 weeks from Day 182 to Day 361		
eDiary collection of EQ-5D-5L ¹⁸		X			X	X	X	X	X
eDiary collection of WPAI:ILI		eDiary prompts ¹⁹							
Recording of unsolicited AEs		X	X	X					

Visit Number		1	2	3	4	5	6	7	USV
Type of Visit/Contact	C	C	SC	C ¹ /SC	SC	SC	SC	SC	C
Month Timepoint				M1	M3	M6	M9	M12	Up to M12
Study Visit	Screening ²	D1 (Baseline)	D8	D29	D91	D181	D271	D361/EoS	USV
Window Allowance (Days)	-28	N/A	±2	-7 to +3	±5	±14	±14	±14	N/A
Recording of any SAEs, AESIs, and MAAEs, as well as AEs that led to discontinuation and relevant concomitant medications/procedures ²⁰		X	X	X	X	X	X	X	X
Recording of concomitant medications and nonstudy vaccinations ²¹		X	X	X	X	X	X	X	
Recording of hospitalizations and outpatient treatment related to or for the treatment of the MAAE or SAE ²¹		X	X	X	X	X	X	X	X
Study completion								X	

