- A point-of-care urine pregnancy test will be performed at the Screening visit and before the vaccine dose on Day 1, if Day 1 is not on the same day as the Screening visit. At the discretion of the Investigator, a pregnancy test either via blood or point-of-care urine can be performed at any time. The participant's follicle-stimulating hormone level may be measured at the Screening visit, as necessary, and at the discretion of the Investigator, to confirm postmenopausal status.
- In a subset of participants, samples will be collected for immunogenicity assessment and immune assessments. Of the people who participate in the subset, an additional blood sample collection for transcriptomics will be optional. Samples on Day 1 must be collected prior to receipt of vaccination.
- Sample collection for future research, including genomics, is optional. Samples on Day 1 must be collected prior to receipt of vaccination.

9. See [Section 4.1](#) for dose levels and vaccination groups. All participants will be randomized to receive a single IM injection.
10. Assessment of EFS will only be performed for participants aged 65 years and older.
11. The NP swab specimen(s) for pathogens, including influenza virus and other respiratory pathogens (eg, SARS-CoV-2) will be collected any time from Day 1 to Day 361 (Month 12)/EoS if participants have protocol-defined ILI per the ILI Case Definitions in [Section 8.10.5](#), or if deemed necessary per Investigator's discretion when influenza is suspected. If participants experience ILI symptoms, they will be instructed to contact the clinic to determine if they need an NP swab collected for testing. NP swab collection should occur within 72 hours of symptom onset. NP swabs should be collected prior to any antiviral therapy, if possible. NP swabs may be collected as part of a home visit in lieu of a clinic visit. In the event that NP swabs during ILI cannot be collected, any available influenza testing results performed outside of the study should be captured in the eCRF.
12. Only for those participants not in the immune response biomarker subset who otherwise would have a clinic visit this day.

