13. The eDiary entries will be recorded at approximately 30 minutes after injection while at the clinic with instruction provided by the clinic staff. Study participants will continue to record in the eDiary for solicited ARs each day after they leave the clinic, preferably in the evening and at the same time each day, on the day of injection and the subsequent 6 days following injection. See [Section 8.9.4](#) for additional details.
14. The site staff will review Symptom Reporting eDiaries daily and if illness symptoms are noted they should follow up with participants to determine if the symptoms warrant the participant providing an NP swab. Follow-up with the participant for symptoms review should be documented in eCRF.
15. The Symptom Reporting eDiary will be activated for collection of ILI symptoms starting at Day 1 and lasting until Day 361 (Month 12)/EoS.
16. Participants will be instructed to report via Symptom Reporting eDiary or telephone calls whether ILI symptoms have been experienced. If participants experience ILI symptoms, they will be instructed to contact the clinic as soon as possible to determine if an NP swab needs to be collected. NP swabs for testing should be collected within 72 hours of symptom onset. NP swabs should be collected prior to any antiviral therapy, if possible. NP swabs may be collected as part of a home visit in lieu of a clinic visit.
17. Telephone/electronic contacts are to remind participants of ILI eDiary reporting, not to capture AEs.
18. For participants reporting symptoms of ILI in the Symptom Reporting eDiary, the EQ-5D-5L responses will be collected using the eDiary on the day of the symptoms reporting (+1 day) and 5 days (+1 day) later.
19. For participants reporting symptoms of ILI in the Symptom Reporting eDiary, the WPAI over the previous 7 days will be collected using the eDiary at 5 days (+1 day) following the start of ILI symptoms reporting in the Symptom Reporting eDiary.
20. Trained study personnel or designee will call all participants to collect information relating to any MAAEs, AEs leading to study discontinuation, SAEs, AESIs, and information on concomitant medications associated with those events. All concomitant medications relevant to or for the treatment of an SAE, AESI, or MAAE will be recorded from Day 1 through Day 361 (Month 12)/EoS.

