3. OBJECTIVES AND ENDPOINTS

The objectives which will be evaluated in this study and endpoints associated with each objective are provided in [Table 2](#).

Table 2: Study Objectives and Endpoints

Primary Objectives	Primary Endpoints

 To evaluate the safety and reactogenicity of mRNA-1010 during the treatment period (28 days after study intervention) and follow-up period (period following the treatment period). 	
 Solicited local and systemic ARs through 7 days after study injection. Unsolicited AEs through 28 days after study injection. MAAEs from Day 1 to Day 361 (Month 12)/EoS. AESIs from Day 1 to Day 361 (Month 12)/EoS. SAEs from Day 1 to Day 361 (Month 12)/EoS. AEs leading to discontinuation from Day 1 to Day 361 (Month 12)/EoS.

 To evaluate relative vaccine efficacy of mRNA-1010 as compared to an active comparator against influenza caused by any influenza A or B virus strains using protocol-defined ILI definition. 	
 First episode of RT-PCR confirmed protocol-defined ILI that begins at least 14 days post vaccination through Day 181 (Month 6)/end of influenza season caused by any seasonal influenza A or B virus strains regardless of antigenic match to strains selected for the seasonal vaccine.
Secondary Objectives	Secondary Endpoints

 To evaluate relative vaccine efficacy of mRNA-1010 vaccine as compared to an active comparator against influenza caused by influenza A or B strains with similarity^a to the vaccine strains, using protocol-defined ILI definition. 	
 First episode of RT-PCR-confirmed protocol defined ILI that begins at least 14 days post vaccination through Day 181 (Month 6)/end of influenza season caused by influenza A or B strains with similarity^a to those selected for the seasonal vaccine.

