For participants aged 65 years and older, frailty will be assessed by clinic staff at baseline using the Edmonton Frail Scale (EFS).

Approximately 1000 participants will be asked to provide blood samples at baseline and on Day 29 (28 days post vaccination) for assessment of immune responses to the study intervention

(immune response biomarker subset). A clinic visit on Day 29 will be required for these participants. All participants will be asked to complete an electronic diary (eDiary) for solicited ARs from Day 1 to Day 7. All participants will be asked to provide an optional blood sample for future research use at Day 1.

There will be 6 safety telephone call visits at Days 8, 29 (except for those participants who are not in the immune response biomarker subset which requires a clinic visit on Day 29), 91, 181, 271, and 361 (Month 12)/EoS as specified in the SoE. The study duration (including screening) is up to 13 months for each participant and the total study duration is approximately 27 months (if 2 influenza seasons are required to perform efficacy analyses).

Participants will be instructed to report whether ILI symptoms have been experienced, via a Symptom Reporting eDiary, twice weekly from Day 1 to Day 181 and once weekly from Day 182 to Day 361 (Month 12)/EoS. If participants experience ILI symptoms, they will be instructed to enter the details in the eDiary and contact the clinic to determine if an NP swab should be collected for RT-PCR testing. NP swabs for testing should be collected within 72 hours of symptom onset. Sites should also reach out to participants if illness symptoms are noted upon review of the eDiary to assess whether the participant is required to provide an NP swab.

NP swab should be collected prior to any antiviral therapy if possible. NP swabs may be collected as part of a home visit in lieu of a clinic visit. In the event that NP swabs during ILI cannot be collected, any available influenza testing results performed outside of the study should be captured in the electronic case report form (eCRF).

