8.9.6. Recording and Follow-up of an AE and/or SAE

The Investigator is responsible for ensuring that all AEs and SAEs are recorded in the eCRF and reported to the Sponsor.

Solicited ARs will be collected from Day 1 through 7 days after the study intervention (ie, the day of injection and 6 subsequent days). Other (unsolicited) AEs will be collected from Day 1 through 28 days after the study intervention (ie, the day of injection and 27 subsequent days).

MAAEs, SAEs, and AESIs will be collected from participants as specified in the SoE (Table 1) from Day 1 until the end of their participation in the study.

At every clinic visit or telephone contact, participants will be asked a standard question to elicit any medically related changes in their well-being (including surveillance for respiratory viral infection symptoms) according to the scripts provided. Participants will also be asked if they have been hospitalized, had any accidents, used any new medications, changed concomitant medication regimens (both prescription and over-the-counter medications), or had any non-study vaccinations.

In addition to participant observations, physical examination findings and other documents relevant to participant safety classified as an AE will be documented on the AE page of the eCRF.

After the initial AE/SAE report, the Investigator is required to proactively follow each participant at subsequent visits/contacts. All AEs and SAEs will be treated as medically appropriate and followed until resolution, stabilization, the event is otherwise explained, or the participant is LTFU (as defined in Section 7.2).

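### The Day 29 contact that closes the 28-day unsolicited-AE period may be made from Day 22, so up to 6 of the 28 days of a primary safety endpoint can pass without scheduled AE inquiry

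*Protocol*

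**What the plan says.** Protocol Section 3 lists "Unsolicited AEs through 28 days after study injection" among the primary safety endpoints. Section 8.9.6 says "Other (unsolicited) AEs will be collected from Day 1 through 28 days after the study intervention" and counts this as the injection day and the 27 days after it. SAP 6.1.7 uses the same period as its primary safety analysis period for unsolicited AEs.

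In the Schedule of Events (Protocol Table 1, repeated as SAP Table 6), the row "Recording of unsolicited AEs" is marked at Days 1, 8 and 29 and nowhere later. The Day 29 column allows -7 to +3 days. That one column serves two purposes: the blood draw in the biomarker subset of about 1000 people, and the safety contact for everyone. The following safety call is Day 91, with ±5 days. Note 17 to the schedule says of the weekly contacts: "Telephone/electronic contacts are to remind participants of ILI eDiary reporting, not to capture AEs".

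SAP 6.7.2 takes percentages over the Safety Set. The SAP has no rule for a participant whose Day 29 contact fell before the period ended.

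The documents also disagree on who gets the Day 29 call. Protocol 4.1 plans it "except for those participants who are not in the immune response biomarker subset which requires a clinic visit on Day 29". The synopsis plans it "except for those participants in the immune response biomarker subset which requires a clinic visit on Day 29", and SAP 4.1 agrees with the synopsis. Note 12 describes the call as "Only for those participants not in the immune response biomarker subset who otherwise would have a clinic visit this day".

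**The concern.** A window that opens a week early may suit a titer sample. It does not suit a contact whose job is to ask about a period that must already be over. A site that calls on Day 22 has followed the protocol, and the schedule gives it no further prompt to ask about ordinary unsolicited AEs. The SAP then counts that participant as observed through Day 28.

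What is at stake is the completeness of the 28-day AE frequencies, which are a primary output of the trial. The exposed events are those that depend on someone asking: non-serious, not medically attended, with onset on Days 23 to 28.

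**Working it through.** The documents state no figure for this shortfall, so there is none to reproduce. The check is study-day arithmetic.

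**Inputs.** Injection is Day 1. The AE period is the injection day plus 27 days (Protocol 8.9.6). The Day 29 window is -7 to +3 and the Day 91 window is ±5 (Protocol Table 1).

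**End of the period.** 1 + 27 = Day 28.

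**Permitted contact days.** 29 - 7 = Day 22 to 29 + 3 = Day 32, which is 11 days. Six of them (Days 22 to 27) fall before Day 28.

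**Full days left after a contact on day d.** max(0, 28 - d):

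| Contact day | 22 | 23 | 24 | 25 | 26 | 27 | 28 to 32 |
|---|---|---|---|---|---|---|---|
| Full days left | 6 | 5 | 4 | 3 | 2 | 1 | 0 |

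The worst case is 6/28 = 21.4% of the period. Counting the rest of the contact day as well makes it 7 days.

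**Average.** This needs the distribution of contact days, which the documents do not give. If contacts were spread evenly over the 11 days (an assumption), the mean would be (6+5+4+3+2+1)/11 = 21/11 = 1.9 days, and 1.9/28 = 6.8%. If every contact fell on Day 28 or later, it would be 0. If every contact fell on Day 22, it would be 21.4%.

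**Recall at the next scheduled call.** The Day 91 call falls on Days 86 to 96. An event starting on Days 23 to 28 would then be recalled after 86 - 28 = 58 days at the least and 96 - 23 = 73 days at the most.

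**The case against.** The strongest reply is that these days are not unobserved. Protocol 8.9.6 has a standard question about changes in well-being at every visit or telephone contact. Section 8.9.3 has the safety-call script ask about AEs. Section 8.9.4 tells participants to call the site at once with any condition. Section 8.9.7 has all unsolicited AEs reported during the study recorded with time of onset. A Day 25 event first mentioned on Day 91 can therefore still enter the 28-day tables. SAEs, MAAEs, AESIs and AEs leading to discontinuation are collected to Day 361. Both arms share one schedule under an observer-blind design, so no bias between arms follows. Percentages over the full Safety Set are ordinary practice.

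All of this stands, and it limits the point. It does not remove it. Spontaneous reporting is passive and the Day 91 call relies on about two months of recall. Schedule note 20, which describes the calls, names MAAEs, SAEs, AESIs and AEs leading to discontinuation but not ordinary unsolicited AEs.

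Timing is a further objection. Vaccination was planned for the 2022/2023 campaign, and the SAP dates Amendment 1 to 02 February 2023, so by inference many Day 29 contacts had already been made. However, Protocol 4.1 allows enrollment to extend over further seasons, and the schedule would apply again.

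A reader might draw two stronger conclusions that the documents do not support.

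- **That Protocol 4.1 cancels the Day 29 call for everyone outside the subset.** Its literal wording does. But the same sentence refers to the subset's clinic visit as the reason and defers to the Schedule of Events. The synopsis, schedule note 12 and SAP 4.1 all say the opposite. This is a drafting contradiction, not the plan.
- **That an early contact also truncates the record behind Per-Protocol membership.** Protocol 6.5.1 records non-study vaccinations through Day 361. It also records systemic steroids, immunosuppressants, immunoglobulins, long-acting biologics and blood products throughout the study after vaccination. Table 1 marks the concomitant medication and vaccination row at every scheduled contact to Day 361.

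**Conclusion.** The point holds as a gap in scheduled collection. A protocol-compliant contact can leave up to 6 of 28 days (21%) of a primary safety endpoint without scheduled AE inquiry inside the period, and the SAP does not distinguish such participants. The actual loss cannot be stated from the documents. The 6.8% average rests wholly on the even-spread assumption, and days without inquiry are not the same as events lost. The exposure is mainly non-serious AEs without medical attendance starting on Days 23 to 28, some of which may be recovered later. Any under-counting should be similar in the two arms, so the effect is on absolute frequencies rather than on the comparison. It would go too far to say that the endpoint is certain to be incomplete.

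**What to change.** Split the Day 29 column by purpose. Keep -7 to +3 for the subset blood draw. Require the contact that closes unsolicited-AE collection to take place on or after Day 29. Where a subset clinic visit falls earlier, complete AE collection by telephone after Day 28. Make the same change in SAP Table 6.

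As a separate drafting correction, reconcile Protocol 4.1 with the synopsis, schedule note 12 and SAP 4.1 on who receives the Day 29 call.

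The cost is protocol wording, visit-window programming and one short extra call for subset participants seen early. If the +3 limit stays, the days allowed for the closing contact fall from 11 to 4 (Days 29 to 32), which sites would need to plan for. No treatment, endpoint or sample size changes.

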8.9.7. Reporting Adverse Events

The Investigator is responsible for reporting all AEs that are observed or reported during the study, regardless of their relationship to the study intervention or their clinical significance. If there is any doubt as to whether a clinical observation is an AE, the event should be reported.

All unsolicited AEs reported or observed during the study will be recorded on the AE page of the eCRF. Information to be collected includes, type of event, time of onset, Investigator-specified assessment of severity (impact on activities of daily living) and relationship to study intervention, time of resolution of the event, seriousness, as well as any required treatment or evaluations, and outcome. The unsolicited AEs resulting from concurrent illnesses, reactions to concurrent illnesses, reactions to concurrent medications, or progression of disease states must also be reported. All AEs will be followed until they are resolved or stable or judged by the Investigator to be not clinically significant. The Medical Dictionary for Regulatory Activities (MedDRA) will be used to code all unsolicited AEs.

Refer to Section 8.9.9 for reporting of medical occurrences that begin before the start of study intervention administration but after obtaining informed consent.

8.9.8. Reporting Serious Adverse Events

Any AE considered serious by the Investigator or that meets SAE criteria (Section 8.10.2) must be reported to the Sponsor immediately (within 24 hours of becoming aware of the SAE). The Investigator will assess whether there is a reasonable possibility that the study intervention caused the SAE. The Sponsor will be responsible for notifying the relevant regulatory authorities of any SAE as outlined in the 21 US CFR Parts 312 and 320. The Investigator is responsible for notifying the institutional review board (IRB) or independent ethics committee (IEC) directly.

If the eCRF is unavailable at the time of the SAE, the paper SAE/AESI Report Form distributed to the study sites should be completed and sent via email or fax as provided on the form.

Regulatory reporting requirements for SAEs are described in Section 8.9.11.

The Investigator and any qualified designees are responsible for detecting, documenting, and recording events that meet the definition of an AE, including SAEs, and remain responsible for following up AEs that are serious, considered related to the study intervention or study procedures, or that caused the participant to discontinue the study.

